2.1.1 All patients analysis set

This analysis set comprises all patients screened for the study and will be used for reporting of disposition and possible screening failures.

2.1.2 Full analysis set

All patients who received at least one dose of IP will be included in the full analysis set. Patients will be classified according to the treatment they were assigned.

Except for summaries of pharmacokinetic (PK) data, all demographic and baseline characteristics, safety, efficacy, patient reported outcome, healthcare resource utilisation, and anti-drug antibodies (ADA) analyses will be based on this analysis set.

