8.3.1 Full analysis set

All patients who received at least 1 dose of IP will be included in the full analysis set. Patients will be classified according to the treatment to which they were randomized or assigned.

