2.2 Violations and deviations

Patients who do not meet eligibility criteria but are randomised will be analysed according to the analysis sets described in Section 2.1. There is no intention to perform a per-protocol analysis in BORA.

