2.2.1 Important protocol deviations

The important protocol deviations are important in that they may significantly affect the assessments of the study safety outcomes.

The final list of protocol deviations will be reviewed, finalised and documented prior to database lock. Only important protocol deviations will be listed and tabulated in the Clinical Study Report (CSR). The following categories of protocol deviations will be reviewed by medical advisors and statisticians prior to database lock to determine those which are considered important deviations:

- Patients who do not meet the inclusion criteria
- Patients who meet any of the exclusion criteria
- Concomitant use of disallowed medications (to be identified through programming). Patients who use one or more disallowed medication (for any reason, unless otherwise specified) during the treatment period will be classed as protocol deviators
- Patients who received the incorrect study dose regimen
- Patients who developed withdrawal criteria during the study but were not withdrawn

Any patients with anomalies in the plasma concentrations, determined as follows, will be flagged and discussed in the CSR:

- Patients for whom all collected plasma concentration levels are persistently below the LLOQ (3.86 ng/ML) throughout the treatment period
- Patients with plasma concentrations in excess of what is considered to be physiologically possible with dosing (ie concentrations $\geq 12,000$ ng/ML)

A listing will be prepared for these patients highlighting the PK sampling times along with their results from the ADA and eosinophil assessments.

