4. ANALYSIS METHODS

4.1 General principles

The age group classification for adult and adolescent from the predecessor studies will be used in the BORA subgroup analysis. If the patient's age at the time of enrolment in the previous study was between 12 and 17 years old then he/she was considered as part of the adolescent group even if the patient was 18 years old at the time of entry in to BORA study. If it was between 18 and 75 years old, he/she was considered as part of adult group. Actual age calculated at BORA study entry will be used in descriptive summary of age and listings.

Patients randomised to placebo in the predecessor study will be summarised separately from patients randomised to benralizumab. The presentation of treatment group will combine treatment assigned in both BORA and the predecessor study as follows:

- Benra 30 mg q.4 weeks
 - Predecessor q.4 weeks
 - Predecessor placebo
- Benra 30 mg q.8 weeks

- Predecessor q.8 weeks
- Predecessor placebo

The analysis of the primary and secondary endpoints will include all data captured during the study, unless the patient withdraws consent, and assent, where applicable, regardless of whether study treatment was prematurely discontinued or delayed, and/or irrespective of protocol adherence. Any data collected after a patient is transitioned into the long-term extension study MELTEMI will not be included in the analyses described in this SAP.

Summary data will be presented in tabular format by treatment. Categorical data will be summarised by the number and percentage of patients in each category. Continuous variables for parametric data will be summarised by descriptive statistics including n, mean, standard deviation, median, minimum value and maximum value unless otherwise specified.

All endpoints as describe in previous sections will be summarised descriptively. The study is not a confirmatory study, thus in general no hypothesis testing and/or p-values will be provided. Following are sets of planned groups for the study.

The primary source of data for the clinical study report (CSR) summaries will be based on patients who stayed in the BORA study. The analyses will follow the two phases as described in the protocol amendment. Some selective summaries will be separately presented for the patients who enrolled into MELTEMI study.

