4.2.5 Analysis methods for safety variables

All safety variables will be summarised for the full analysis set.

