4.2.5.1 Adverse events

Adverse events (AEs) will be summarised separately by the treatment group for the on-study, on-treatment and post-treatment periods, as defined in Section 3.1.1.

An overall summary table will be produced showing the number and percentage of patients with at least 1 AE in any of the following categories; AEs, serious adverse events (SAEs), deaths due to AE, and AEs causing discontinuation of the investigational product (DAEs). This summary will also be repeated by baseline blood eosinophil count ($<300/\mu\text{L}$, $\geq 300/\mu\text{L}$) for the on-study and on-treatment periods. The total number of AEs in the different AE categories in terms of AE counts will also be presented (ie, accounting for multiple occurrences of the same event in a patient).

AEs will be summarised by System Organ Class (SOC) and Preferred Term (PT) assigned to the event by MedDRA. For each PT, the number and percentage of patients reporting at least one occurrence will be presented, ie, for a patient multiple occurrences of an AE will only be counted once.

A summary of the most common (frequency of $\geq 5\%$ in any treatment group) AEs will be presented by PT. AEs (by PT) will be summarised by causality and maximum intensity. If a patient reports multiple occurrences of the same AE, the maximum intensity will be taken as the highest recorded maximum intensity (the order being mild, moderate, and severe). SAEs, DAEs, and deaths will also be summarised in separate tables.

Furthermore, events of interests such as injection site adverse events, hypersensitivity adverse events, adjudicated MACE+, and malignancies will be summarised separately.

The rate of AEs per person-years at risk, calculated as (number of patients reporting AE)/(total period with patients at risk of AE), will be reported for the on-study, post-treatment and on-treatment periods. The total period at risk for each patient within each study period will follow the definitions specified in Sections 3.1.1. Rates will typically be expressed in terms of events per 100 patient-years.

Separate listings of patients with AEs, SAEs, death due to AE, discontinuations due to AEs, as well as events of interest will be presented.

For the patients who rolled over to MELTEMI study, selective AE and SAE tables during study period will be summarised by treatment group. A listing of adjudicated MACE+ and malignancies will be also provided.

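### Safety, ADA and exposure tables group patients by assigned regimen, so events in anyone dosed on the other regimen are reported under the one not received; the numbers are probably small and the fix is cheap

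*SAP*

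**What the plan says.** SAP 2.1.2 defines the full analysis set as everyone given at least one dose and adds: "Patients will be classified according to the treatment they were assigned". The same section puts safety, efficacy, patient-reported outcome, resource-use and ADA analyses on this set. Protocol 8.3.1 agrees: "Patients will be classified according to the treatment to which they were randomized or assigned". SAP 4.2.5 confirms it for safety: "All safety variables will be summarised for the full analysis set". SAP 4.2.4 uses the same set for exposure.

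Table columns follow the same principle. SAP 4.1 states: "The presentation of treatment group will combine treatment assigned in both BORA and the predecessor study as follows". SAP 4.2.5.1 then applies them: "Adverse events (AEs) will be summarised separately by the treatment group for the on-study, on-treatment and post-treatment periods".

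SAP 2.2.1 describes important deviations as those that could materially affect how the study's safety outcomes are assessed. Among the categories to be reviewed it names "Patients who received the incorrect study dose regimen". Deviations judged important are listed and tabulated in the study report. Nothing in that section, or elsewhere, moves such a patient to another column. On a per-protocol set, SAP 2.2 says: "There is no intention to perform a per-protocol analysis in BORA". Protocol 8.5.3 marks sensitivity analysis as not applicable.

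**The concern.** Grouping by assigned treatment is the usual choice for efficacy. For safety, the usual question is what happened to patients on the dosing they actually had. There is no placebo arm in this extension, so dosing frequency is the only treatment contrast the tables can show. A patient assigned to every 8 weeks (Q8W) who was given active drug at the interim visits would have all adverse events, laboratory values and ADA results reported as Q8W experience, and the reverse holds for a Q4W patient.

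Two things are at stake. Mixing of this kind pulls the two regimens' profiles towards each other. For events counted in single digits, it can also put a case in the wrong column.

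The SAP protects one set of summaries against this sort of problem: the PK analysis set (SAP 2.1.3) is limited to patients whose samples are taken to be unaffected by factors such as protocol violations. The tables that serve the primary objective have no counterpart.

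**Working it through.** **No plan figure to reproduce.** The minimum of 1200 patients (SAP 1.3) is a judgement, with no error rate, power or formula behind it, and the study is not powered for any test. The main check is therefore of the text: SAP 2.1.2, 4.1, 4.2.4 and 4.2.5 and Protocol 8.3.1 all point to assigned treatment, and no section overrides them for safety.

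**Size, on assumed inputs.** Let a fraction m of each assigned arm have received the other regimen throughout, and let p1 and p2 be the true event risks on the two regimens.

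- Observed risk in arm 1 = (1 − m)·p1 + m·p2
- Observed risk in arm 2 = (1 − m)·p2 + m·p1
- Observed difference = (1 − 2m)·(p1 − p2)

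The fraction m and the risks are not in the documents. The illustration takes p1 = 10% and p2 = 5%, with counts out of 1200:

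| m | Patients of 1200 | Observed risks | Observed difference (points) | Share of true difference kept |
|---|---|---|---|---|
| 0.1% | 1.2 | 9.995% vs 5.005% | 4.99 | 0.998 |
| 0.5% | 6 | 9.975% vs 5.025% | 4.95 | 0.99 |
| 1% | 12 | 9.95% vs 5.05% | 4.90 | 0.98 |
| 2% | 24 | 9.90% vs 5.10% | 4.80 | 0.96 |
| 3% | 36 | 9.85% vs 5.15% | 4.70 | 0.94 |

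For m from 0.1% to 3%, the true difference shrinks by 0.2% to 6% of itself. With unequal fractions m1 and m2, the factor is 1 − m1 − m2.

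**Small columns.** SAP 4.1 splits each regimen by predecessor assignment, and SAP 4.1.1 also summarises adolescents separately. One patient is 1/600 = 0.17 percentage points in a column of 600, 1/50 = 2.0 in a column of 50 and 1/20 = 5.0 in a column of 20 (column sizes assumed). In the column of 20, a single patient is enough to reach the 5% threshold for the common-event table in SAP 4.2.5.1.

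**Can the regimens be told apart in the records?** Adults have 14 dosing visits, Weeks 0 to 52. Q4W gives 14 active injections. Q8W after predecessor placebo gives 8 (Weeks 0, 4, 8, 16, 24, 32, 40 and 48). Continuing Q8W gives 7 if active drug falls at Week 0. Every active Q8W injection also falls on a Q4W visit, so the regimens differ only at the interim visits: active under Q4W, dummy under Q8W. After predecessor placebo, the first three doses are active under both, and the regimens first differ at Week 12 (Protocol 4.2.3.1).

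**The case against.** The strongest case against is that this will rarely happen and will change little. Dosing is directed by an IVRS call at each dosing visit (Protocol 1.5, notes to Figure 1), and injections are given on site by study staff and recorded (Protocol 6.8). A full-course swap would need that system to fail repeatedly. Both regimens are 30 mg of active drug, so an error misstates frequency and cannot charge active-drug events to placebo. The study is descriptive, and a shift from 10% vs 5% to 9.95% vs 5.05% would not alter a conclusion. Wrong-regimen cases judged important appear in the report, patient listings cover serious events and events of interest, and cardiovascular events and malignancies are adjudicated.

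Most of this stands, and it limits the weight of the point. It does not answer it. Listings let a careful reader trace a case, but they leave the counts and denominators uncorrected, and in a descriptive study the tables are the result.

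Three stronger readings are tempting, and the documents do not support them:

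- A reader might infer that the SAP expects wrong-regimen dosing. It only foresees it, as one category in a review list with no frequency.
- A reader might take a crossover of one or more per cent as likely. Nothing in the documents supports any rate.
- A reader might treat the absence of a per-protocol set as a second defect. Excluding deviators would remove adverse events from the safety tables, which is not what is needed.

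**Conclusion.** The point holds as a gap in the classification rule. Safety, ADA and exposure are grouped by assigned regimen in a study whose primary objective is the safety of two regimens, and the plan's own deviation category has no effect on those tables.

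The likely numerical effect is small. A shrinkage of 0.2% to 6% of any true difference rests on assumed full crossover of 0.1% to 3%, equal in both arms; the real number could be zero. The practical risk lies in rare events and in the small adolescent and predecessor-placebo columns, where one patient can be visible. The change is worth making because it bears on the primary objective and uses dosing data already collected, not because a material bias has been shown.

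**What to change.** Add a regimen-received classification to SAP 2.1.2 and use it for the safety, ADA and exposure tables:

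- Keep the assigned regimen unless dosing records show that the other regimen was received throughout.
- Judge this on the injections given at the interim visits where the regimens differ (active or placebo), ignoring missed injections. EU adolescents have no dummy injection at interim visits after the first three doses, so there the question is whether active drug was given at all.
- Patients who stop before the regimens diverge stay as assigned.
- Footnote every reclassified patient, and flag isolated dosing errors in the listings without reclassifying.
- Keep assigned regimen for efficacy and patient-reported outcomes.

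A rule based on the majority of active injections would not work, because all active Q8W injections also fit the Q4W schedule.

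The cost is a paragraph in the SAP and a derivation from the dosing records, with a little more care than a simple count. The column scheme in SAP 4.1 has no cell for a continuing patient who received the other regimen in BORA, so the table shells must say where such a patient is shown. The downside is that a few patients may sit in different columns in the safety and efficacy tables, which the footnote explains.

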2.1.3 PK analysis set

All patients who received benralizumab, from whom PK blood samples are assumed not to be affected by factors such as protocol violations, and who had at least 1 quantifiable serum PK observation post the first dose will be included in the PK analysis dataset. All PK summaries will be based on this analysis set.

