Eosinophils are a prominent feature of the inflammatory response to helminthic parasitic infections, and the presence of infiltrating eosinophils has been circumstantially associated with a positive prognosis in certain solid tumors. Therefore, there is a theoretical risk that prolonged eosinophil depletion may diminish the ability to defend against helminthic parasites, or negatively impact the natural history of certain malignant tumors. Risk minimization measures include exclusion of patients with untreated parasitic infection and active or recent malignancy, in conjunction with the performance of routine pharmacovigilance activities. In addition, the development of anti-drug antibodies (ADA) to benralizumab has been documented. Theoretical risks of developing ADA include decreased drug efficacy and hypersensitivity reactions (eg, anaphylaxis or immune complex disease).

A detailed assessment of the risk/benefit of benralizumab in patients with asthma is provided in the Investigator's Brochure.

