4.2.9 Analysis methods for pharmacokinetic variables

The PK analyses will be performed at or under the guidance of AstraZeneca Research and Development. Benralizumab serum concentrations will be summarised using descriptive statistics at each visit by treatment group using PK analysis set.

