4.2.10 Analysis method for immunogenicity variables

Demographic and patient characteristics including age, sex, race, ethnicity group and BMI subgroups ($\leq 35 \text{ kg/m}^2$, $> 35 \text{ kg/m}^2$) by ADA status (positive, negative) and ADA positive subgroups (stable persistently positive, nAb positive) will be presented by treatment group.

The number and percentage of patients within each ADA response category defined in Section 3.6 will be summarised by treatment group and ADA status in predecessor studies. Anti-drug antibody response and the corresponding titre will be summarised by visits. In addition, the ADA response will be presented cumulatively by visit. A summary of ADA titres over time by ADA status (ADA positive patients at any visit, ADA newly persistently positive, ADA stable persistent positive, and nAb positive patients) will be provided to monitor titre changes over time.

Newly persistently positive ADA response and ADA stable persistently positive by maximum titer quartile subgroups will be presented by treatment group. A table will be presented to list patients in each treatment group with treatment boosted ADA, and repeated for those patients with maximum titer above the 3rd quartile. For each patient, the table will list the titre at study baseline, maximum titre, and the fold-change that is above the 3rd quartile of the maximum titre from baseline. Similar summaries will be provided for patients with decrease in titre

including the baseline titre, maximum titre, post maximum titre that is decreased >75% from the maximum titre, and its percent reduction from the maximum titre.

The relationship among the following parameters with ADA status (positive, negative) and ADA positive subgroups (ADA titre greater than median of the maximum, newly persistently positive, stable persistently positive, nAb positive) will be presented, unless stated otherwise.

- The annual exacerbation rate during on-study period, on-treatment period and post-treatment period
- Change from baseline in pre-BD FEV₁ for each post-baseline visit
- Adverse events (AEs) and serious adverse events (SAEs) by System Organ Class (SOC) and Preferred Term (PT), AEs and SAEs by preferred term, AEs and SAEs by PT and causality, and hypersensitivity events by PT and causality. These summaries will be conducted during on-treatment period. Additional AE summaries may be added as needed, based on review of the pre-specified summaries

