- Absolute blood eosinophil counts (cells/ μ L) for each visit
- Benralizumab serum concentrations for each visit

The following plots will be provided:

- Percentage of Anti-Drug Antibody positive patients by visit
- Anti-Drug antibody titres by visit
- Median blood eosinophil counts profile by (1) treatment groups and ADA subgroup (ADA positive and ADA negative), and (2) by ADA subgroups (ADA positive, ADA negative, newly persistently ADA positive, stable persistently ADA positive, ADA with titer > median of maximum titre, ADA with titer > 3rd quartile of maximum titre) for each treatment group.

Note data from adolescents will not be plotted for the median blood eosinophil counts.

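### The serum-concentration-by-ADA table appears to leave out dosed patients who are below LLOQ at every sample, while the other ADA tables keep them (minor)

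*SAP*

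**What the plan says.** Four parts of the SAP bear on this.

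- **Entry to the PK set (SAP 2.1.3; same rule in Protocol 8.3.2).** A treated patient enters only if samples are not compromised, for example by protocol violations, and if the patient is one "who had at least 1 quantifiable serum PK observation post the first dose will be included in the PK analysis dataset". The section closes: "All PK summaries will be based on this analysis set".
- **Reach of the full analysis set (SAP 2.1.2).** ADA analyses use the full analysis set, but the sentence that says so begins with a carve-out: "Except for summaries of pharmacokinetic (PK) data, all demographic and baseline characteristics".
- **The tables.** SAP 4.2.9 ties the by-treatment summary to the PK set: "Benralizumab serum concentrations will be summarised using descriptive statistics at each visit by treatment group using PK analysis set". SAP 4.2.10 plans to present "The relationship among the following parameters with ADA status (positive, negative) and ADA positive subgroups", and one listed parameter is "Benralizumab serum concentrations for each visit". No analysis set is named there.
- **Patients with no measurable drug (SAP 2.2.1).** One group to be flagged and discussed in the CSR is "Patients for whom all collected plasma concentration levels are persistently below the LLOQ", with the limit given as 3.86 ng/mL. A listing will show their PK sampling times with ADA and eosinophil results.

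**The concern.** Membership of the PK set depends on the quantity the table summarises. The concentration-by-ADA table is where a reader would look to see whether exposure at the fixed dose is lower in ADA-positive or nAb-positive patients. The entry rule removes the patients whose measured exposure was lowest. The protocol gives a reason to care: "Theoretical risks of developing ADA include decreased drug efficacy and hypersensitivity reactions" (Protocol 1.4), and PK and immunogenicity form a stated secondary objective.

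There is also a mismatch between related tables. Titre, eosinophils, exacerbations and adverse events by ADA status rest on the full analysis set. A reader comparing eosinophils with concentrations in the same nAb-positive stratum could be looking at two different groups of patients without being told.

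**Working it through.** The plan states no figure to reproduce. The check is a reading of the text followed by an illustration.

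**Which set governs the table**

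1. SAP 4.2.10 names no set, so the general rules apply.
2. SAP 2.1.2 sends ADA analyses to the full analysis set but excepts summaries of PK data.
3. Serum concentration by visit is a summary of PK data, and SAP 2.1.3 claims all such summaries for the PK set.
4. The PK set is therefore the better reading, although the text does not settle it.
5. A patient quantifiable even once after the first dose stays in. Only patients below LLOQ at every post-first-dose sample drop out.
6. No rule is given for below-LLOQ concentrations. The rule in SAP 3.1.2 for values reported with a less-than sign is written for laboratory variables.

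**Effect within one ADA stratum**

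Let f be the share of the stratum that is below LLOQ at every sample, and G the mean in the rest. Both are assumptions, as the documents give neither.

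- PK-set mean: G.
- All-dosed mean with below-LLOQ values set to 0: (1-f) x G + f x 0 = (1-f)G.
- Overstatement: G / [(1-f)G] = 1/(1-f), whatever G is.
- Median: removing the lowest share f means the reported median is the full stratum's quantile f + (1-f)/2 = (1+f)/2.

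| f | 1/(1-f) | reported median is the full stratum's |
|---|---|---|
| 5% | 1/0.95 = 1.05 | 52.5th percentile |
| 10% | 1/0.90 = 1.11 | 55th percentile |
| 20% | 1/0.80 = 1.25 | 60th percentile |
| 30% | 1/0.70 = 1.43 | 65th percentile |

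A geometric mean would be more sensitive. With G now the geometric mean in the rest, and below-LLOQ values set to 3.86/2 = 1.93 ng/mL, the overstatement is (G/1.93)^f. At f=10% this is 1.48, 1.66 and 1.87 for G = 100, 300 and 1000 ng/mL. SAP 4.1 plans means and medians and does not name geometric means, so this is only a caution.

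**Effect on the ADA contrast**

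Write f+ and f- for the shares in ADA-positive and ADA-negative patients. The all-dosed ratio of means is (1-f+)G+ / [(1-f-)G-], and the PK-set ratio is G+/G-. The table therefore multiplies the true positive-to-negative ratio by (1-f-)/(1-f+).

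- f+ = 20%, f- = 0: 1.00/0.80 = 1.25. A lower exposure in ADA-positive patients looks smaller than it was.
- f+ = f-: 1.00. The ratio is not distorted.
- f+ = 5%, f- = 20%: 0.80/0.95 = 0.84. An ADA effect would be exaggerated.

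The direction is fixed within a stratum, but between strata it depends on figures that the documents do not contain.

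**The case against.** The strongest reply is that the SAP has already dealt with these patients. SAP 2.2.1 identifies them, commits to discussing them in the CSR, and lists their sampling times beside ADA and eosinophil results. That patient-level view is what one needs to tell rapid clearance from a dose not given. This stands, and it largely sets the severity. What a listing does not supply is a denominator, a percentage below LLOQ by ADA subgroup, or a subgroup summary that includes these patients.

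A second reply is that SAP 4.2.10 names no set, so its concentration item could be run on the full analysis set with the other ADA tables. That is possible, but the carve-out in SAP 2.1.2 and the closing sentence of SAP 2.1.3 point the other way. The ambiguity is itself a reason to name the set.

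A third is that the study is descriptive, with no powered hypothesis, and that the other parameters shown by ADA status keep these patients. That also stands.

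Three stronger readings are tempting and should be resisted:

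- **That an all-below-LLOQ profile is the extreme form of an ADA effect.** SAP 2.2.1 classes it as an anomaly, beside concentrations too high to be physiologically possible, and SAP section 2 describes anomalous PK results at a predecessor site with no root cause found. Non-dosing or sample problems could give the same profile.
- **That ADA-negative patients are hardly affected, so the bias runs one way.** No passage gives below-LLOQ frequency by ADA status.
- **That these patients vanish from the report, or that the PK set must be redefined throughout.** The first is contradicted by SAP 2.2.1, and the second goes beyond what one table needs.

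**Conclusion.** The point holds as a minor one. On the better reading of SAP 2.1.2, 2.1.3 and 4.2.10, the concentration-by-ADA table selects patients on the outcome it summarises and does not share a denominator with its companion ADA tables. Within a stratum this can only raise the reported concentration. If all-below-LLOQ patients are more common among ADA-positive or nAb-positive patients, the apparent effect of ADA on exposure shrinks; the documents do not show whether they are.

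The illustrative size, 5% at f=5% and 25% at f=20%, applies to an arithmetic mean with below-LLOQ values set to 0. The true f is unknown and could be very small, since a single quantifiable value keeps a patient in. The consequence is limited to one secondary descriptive table, for patients who are already listed individually.

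**What to change.** Leave the PK set as it is for the main by-treatment concentration summaries in SAP 4.2.9. Then:

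1. In SAP 4.2.10, base the concentration-by-ADA summaries on all benralizumab-treated patients with at least one evaluable post-first-dose PK sample, quantifiable or not. Keep the protocol-violation clause and the exclusion of the closed site. Note the exception in SAP 2.1.3, and record it in SAP section 6, because Protocol 8.3.2 puts all PK summaries on the PK set.
2. Show n (%) below LLOQ by visit and ADA subgroup.
3. Report medians with below-LLOQ values ranked as below LLOQ. Where the median itself falls there, print it as <3.86 ng/mL.

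The cost is SAP wording and a small programming change, with no new data. The downside is that a patient with suspected non-dosing may enter the table. Identify such patients from the SAP 2.2.1 listing and footnote them.
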